The primary clinical question of interest is: What is the intervention effect in percentage of participants achieving EASI-75 after 16 weeks of lebrikizumab 250 mg once every 2 weeks (Q2W) intervention in participants with moderate-to-severe AD, who have been previously treated with dupilumab and who remain on study treatment until Week 16.

The estimand is described by the following attributes:

Population: participants with moderate-to-severe AD who have been previously treated with dupilumab and who remain on study treatment until Week 16.

Further details can be found in Section 5.

Endpoint: Do participants achieve at least 75% improvement from baseline to Week 16 in EASI.

Intercurrent events: There are no intercurrent events for this population since participants who initiate rescue medication are discontinued from the study and hence study treatment. Therefore, participants who stay on study treatment through Week 16 will not have an intercurrent event such as initiating rescue medication or permanently discontinuing treatment.

Population-level summary: Percentage of participants achieving EASI-75 response at Week 16.

Secondary estimand(s)

There is no secondary estimand planned at this stage, however, additional estimand(s) might be specified in the statistical analysis plan (SAP).

Overall Design

Study J2T-MC-KGBO (KGBO) is an open-label, Phase 3b study, which is 24 weeks in treatment duration. The study is designed to evaluate the safety and efficacy of lebrikizumab in adults and adolescents (≥ 12 years to < 18 and weighing ≥ 40 kg) with moderate-to-severe AD and previously treated with dupilumab.

During the 24-week Treatment Period, approximately 120 participants will receive treatment:

- 500 mg subcutaneous (SC) once every 2 weeks (Q2W) loading dose at baseline and Week 2, followed by 250 mg SC Q2W until Week 16.
- Responders, defined as achieving IGA (0,1) or EASI-75 at Week 16, will receive 250 mg SC once every 4 weeks (Q4W).
- Inadequate responders at Week 16 will continue to receive 250 mg SC Q2W.

Brief Summary:

The purpose of this study is to determine the proportion of participants achieving EASI-75 at Week 16 with lebrikizumab in participants with moderate-to-severe AD previously treated with dupilumab.

Study details include:

- The planned study duration will be up to 38 weeks.
- The treatment duration will be up to 24 weeks.

- The visit frequency will be every 2 weeks for the first 2 visits, then every 4 weeks thereafter.

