Participants will be monitored for these events and will be provided appropriate intervention or supportive care as needed. If events occur additional testing and data collection may be required as described further in Sections 8.3.3, 8.3.4, and 8.3.5.

Additionally, to monitor participant safety during the course of the study the sponsor will conduct trial-level safety reviews at periodic intervals throughout the study.

In summary, in the context of the cumulative knowledge for lebrikizumab, the benefit/risk balance is assessed to be acceptable for testing in this Phase 3b study.

More detailed information about the known and expected benefits and risks and reasonably expected AEs of lebrikizumab may be found in the IB or Development Safety Update Report.

3. Objectives, Endpoints, and Estimands

Objectives	Endpoints
Primary	

 To evaluate efficacy of lebrikizumab 250 mg Q2W on reducing signs and symptoms of AD at Week 16 in participants with moderate-to-severe AD previously treated with dupilumab 	
 Percentage of participants achieving EASI-75 at Week 16
Secondary	

 To evaluate the efficacy of lebrikizumab on reducing signs and symptoms of AD at Week 16 and Week 24 in participants with moderate-to-severe AD previously treated with dupilumab 	
 Percentage of participants achieving EASI-75 at Week 24 Percentage of participants with an IGA score of 0 or 1 and a reduction ≥ 2 points from baseline to Weeks 16 and 24 Percentage change EASI from baseline to Weeks 16 and 24 Change in EASI from baseline to Weeks 16 and 24 Percentage of participant achieving EASI-90 from baseline to Weeks 16 and 24 Percentage of participants with a Pruritus NRS of ≥ 4 points at baseline who achieve at least 4-point reduction at Weeks 16 and 24 Percentage of participants with a Pruritus NRS of ≥ 3 points at baseline who achieve at least 3-point reduction at Weeks 16 and 24 Percentage change in Pruritus NRS score from baseline to Weeks 16 and 24 Percentage of participants with a Sleep-Loss Scale of ≥ 2 points at baseline who achieve at least 2-point reduction at Weeks 16 and 24 Change in Sleep-Loss Scale from baseline at Weeks 16 and 24 Percentage of participants with a Skin Pain NRS of ≥ 4 points at baseline who achieve a

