
To discern responder variability within the study and to track response variability to lebrikizumab
	
Changes from baseline in serum proteins related to AD pathogenesis; Refer to Section 10.2, Appendix 2

Abbreviations: AD = atopic dermatitis; ADCT = atopic dermatitis control tool; cDLQI = Children’s Dermatology Life Quality Index; DLQI = Dermatology Life Quality Index; EASI = Eczema Area and Severity Index; EASI-75 = $\geq 75\%$ reduction from baseline in EASI; EASI-90 = $\geq 90\%$ reduction from baseline in EASI; F-IGA = face - investigator’s global assessment; IGA = investigator’s global assessment; mTLSS = Modified Total Lesion Symptom Scale; NRS = numeric rating scale; Q2W = once every 2 weeks; SCORAD = SCORing atopic dermatitis; TCI = topical calcineurin inhibitors, TCS = topical corticosteroid; WPAI-AD = work productivity and activity impairment questionnaire–atopic dermatitis.

NOTE: Endpoints in the table above collected by visit references data collection visits.

Primary estimand

The primary clinical question of interest is: What is the intervention effect in percentage of participants achieving EASI-75 after 16 weeks of lebrikizumab 250 mg once every 2 weeks

(Q2W) intervention in participants with moderate-to-severe AD, who have been previously treated with dupilumab and who remain on study treatment until Week 16.

The estimand is described by the following attributes:

Population: participants with moderate-to-severe AD who have been previously treated with dupilumab and who remain on study treatment until Week 16.

Further details can be found in Section 5.

Endpoint: Do participants achieve at least 75% improvement from baseline to Week 16 in EASI.

Intercurrent events: There are no intercurrent events for this population since participants who initiate rescue medication are discontinued from the study and hence study treatment. Therefore, participants who stay on study treatment through Week 16 will not have an intercurrent event such as initiating rescue medication or permanently discontinuing treatment. Further details on study interventions and concomitant medications, including rescue treatments, can be found in Section 6.8.1.

Population-level summary: Percentage of participants achieving EASI-75 response at Week 16.

Secondary estimand(s)

There is no secondary estimand planned at this stage, however, additional estimand(s) might be specified in the SAP.

4. Study Design

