6.3. Measures to Minimize Bias: Randomization and Blinding

In this open-label study, potential bias will be reduced by specifying treatment response ascertained from all eligible participants and safety reporting. Adherence to the study design requirements, including those specified in the SoA, is essential and required for study conduct.

The site will contact the interactive web-response system (IWRS), prior to the start of study intervention administration and at the primary endpoint for each eligible participant, to provide demographic information and IGA/EASI results, respectively.

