6.8.5. Rescue Medicine for Atopic Dermatitis

To be consistent with real world practice, defined topical medications are allowed in this study (see Section 6.8.4). However, rescue therapies may be needed if the participant experiences intolerable clinical worsening of symptoms. Escalation to high potency topical TCS, topical JAK inhibitors, phototherapy and/or systemic medications (including but not limited to corticosteroids, immunosuppressants, biologics, small molecules, etc.) for the treatment of AD should only occur if participants do not respond adequately after at least 7 days of low/mid potency TCS, TCI and/or topical PDE4 inhibitors. Any use of topical JAKs, phototherapy, and/or systemic medications will be considered rescue therapy. Use of high-potency TCS for more than 10 days is also considered rescue therapy. Participants that receive Rescue therapy must be discontinued from the study. (see Section 7.1).

All rescue medication must be recorded in the CRF.

7. Discontinuation of Study Intervention and Participant Discontinuation/Withdrawal

Discontinuation of specific sites or of the study as a whole are handled as part of Appendix 1.

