## 5.2.1. Primary Estimand for the Primary Endpoint

The primary estimand for the primary endpoint represents the primary clinical question of interest: What is the intervention effect in percentage of participants achieving at least 75% improvement from baseline in Eczema Area and Severity Index (EASI) after 16 weeks of lebrikizumab 250 mg Q2W intervention in participants with moderate-to-severe AD who have been previously treated with dupilumab and who remain on study treatment until Week 16?

The primary estimand for the primary endpoint is described by the following attributes:

- A. Population: participants with moderate-to-severe AD who have been previously treated with dupilumab and who remain on study treatment until Week 16.
- B. Endpoint: whether participants achieve at least 75% improvement from baseline in EASI at Week 16.

- C. Intercurrent events: There are no intercurrent events for this population since participants who initiate rescue medication are discontinued from the study and hence study treatment. Therefore, participants who stay on study treatment through Week 16 will not have an intercurrent event such as initiating rescue medication or permanently discontinuing treatment.
- D. Population-level summary: percentage of participants achieving EASI-75 response at Week 16.

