participants with moderate-to-severe AD who have been previously treated with dupilumab if all participants adhered to treatment?

This estimand is described by the following attributes:

- A. Population: Treatment Period II population as described in Section 5.1.1.
- B. Endpoint: apply to all secondary endpoints at Week 24.
- C. Intercurrent events (ICEs): One ICE, permanent treatment discontinuation, is considered by this estimand as follows:
  - a. For participants who discontinue treatment after Week 16, a hypothetical strategy will be used to estimate what the treatment effect would have been if all subjects continued with treatment. Therefore, a hypothetical strategy is used for this type of ICE.
- D. Population-level summary: Population-level summary: percentage of successful responses or means at Week 24.

Because participants who initiate rescue medication are required to discontinue from the study and hence permanently discontinue study treatment, the supportive estimands for the primary and secondary endpoints only consider permanent treatment discontinuation as an ICE.

Analytical details on how missing data including those as a result of intercurrent events will be handled can be found in Section 5.4. The following table (Table KGBO.5.2) summarizes the analytical strategies that will be conducted on the intercurrent events for the five estimands.

		Analysis Stra Perman Disco	Missing Data		
Estimand	Population	Due to lack of efficacy	Due to any other reasons, including initiation of rescue medication	Imputation Method	
Primary Estimand for the Primary Endpoint and Secondary Endpoints	ITT Population who remained on treatment	Not applicable	Not applicable	Primary analysis: as observed	
Supportive Estimand for the Primary Endpoint and Secondary	ITT Population	Composite: Set to baseline	Hypothetical: Set to missing	MCMC-MI	

Endpoints at Week 16 (Hybrid)				
Supportive Estimand for the Primary Endpoint and Secondary Endpoints at Week 16 (Hypothetical)	ITT Population	Hypothetical: Set to missing	Hypothetical: Set to missing	LOCF
Supportive Estimand for Secondary Endpoints at Week 24 (Hybrid)	Treatment Period II Population	Composite: Set to baseline	Hypothetical: Set to missing	MCMC-MI
Supportive Estimand for Secondary Endpoints at Week 24 (Hypothetical)	Treatment Period II Population	Hypothetical: Set to missing	Hypothetical: Set to missing	LOCF

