### 5.4.1. As Observed Analysis

The "as observed" strategy is used in so-called "observed cases" or "completers" analysis ubiquitous in the literature. For this analysis, only data from completers at the visit are relevant. All efficacy data will be summarized using an "as observed" analysis and summaries based on observed data at each postbaseline visit will be provided.

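### The primary EASI-75 rate is conditional on staying on treatment to Week 16, while the objective and stated purpose carry no such condition, and no planned analysis counts all early leavers as non-responders

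*Protocol*

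**What the plan says.** **Objective and purpose.** The primary objective (Protocol Section 3, repeated in SAP Section 3) is to evaluate efficacy at Week 16 "in participants with moderate-to-severe AD previously treated with dupilumab". The Brief Summary in the Synopsis says: "The purpose of this study is to determine the proportion of participants achieving EASI-75 at Week 16 with lebrikizumab", again in that unrestricted population. Protocol 9.1 restates the objective in the same way.

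**Bias statement.** For this open-label, single-arm design, Protocol 6.3 says "potential bias will be reduced by specifying treatment response ascertained from all eligible participants and safety reporting".

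**Primary estimand.** The clinical question in the Synopsis and Protocol Section 3 is asked in "participants with moderate-to-severe AD, who have been previously treated with dupilumab and who remain on study treatment until Week 16". SAP 5.2.1 defines the population attribute as "A. Population: participants with moderate-to-severe AD who have been previously treated with dupilumab and who remain on study treatment until Week 16", and on that basis declares that there are no intercurrent events. SAP Table KGBO.5.2 gives the analysis population as "ITT Population who remained on treatment", analysed as observed. SAP 5.4.1 adds: "For this analysis, only data from completers at the visit are relevant".

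**Rescue.** Protocol 6.8.5: "Participants that receive Rescue therapy must be discontinued from the study". Protocol 7.1 also lists a need for AD rescue as a reason to stop study drug permanently.

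**Supportive estimands.** SAP 5.2.2 defines two for Week 16, both in the full ITT population. The hybrid sets stops for lack of efficacy to the baseline value and sends all other stops to multiple imputation (MCMC-MI). The hypothetical one sets all stops to missing and applies LOCF. In Table KGBO.5.2, initiation of rescue is placed in the column for reasons other than lack of efficacy.

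**The concern.** Whether a participant belongs to the primary population is settled after treatment starts, and partly by how well treatment works. Someone whose AD worsens enough to need rescue before Week 16 is removed and then counts neither as a responder nor as a non-responder. The objective, the purpose statement and 6.3 give no hint of this condition.

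The denominator matters here because a single-arm rate has no comparator to absorb the selection. Protocol 2.1 intends the result to inform comparison with the dupilumab-naïve population of the pivotal trials. About 80 of the 120 planned participants stopped dupilumab for no, partial or lost response, so a second treatment failure is a central question. A reader who takes the headline rate as the response rate in everyone enrolled would be reading a different quantity.

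The supportive analyses leave a gap at the same place. In the hybrid estimand a participant removed for rescue is set to missing and imputed, so can be imputed as a responder. Under LOCF, a participant who had reached EASI-75 at Week 8 and then stopped for an adverse event is carried forward as a Week 16 responder.

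**Working it through.** **1. The plan's own figure.** Inputs from Protocol 9.5 and SAP 4.2: N = 120 enrolled, anticipated rate 50%, two-sided 90% Wilson interval. With z = 1.645, the half-width is z·√[p(1−p)/n + z²/(4n²)] / (1 + z²/n). At p = 0.5 and n = 120 this is 7.42 points, giving 42.6% to 57.4% as stated. The other four rows of the table also reproduce. The claim of more than 95% probability that the half-width is at most 10 points holds, and would hold down to 65 analysed participants. The sample size is not at issue.

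**2. Effect of the restriction when every leaver is a non-responder.** Let m of N leave before Week 16, d = m/N, and r respond on treatment. The primary rate is r/(N − m). The all-enrolled rate is r/N, which equals the primary rate × (1 − d). The documents give no dropout rate; Protocol 7.2 says only that few discontinuations are expected. The range of 5% to 20% is an assumption.

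Taking 50% on treatment:

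| Leave (assumed) | On treatment | Responders | 90% CI reported | All-enrolled rate |
|---|---|---|---|---|
| 5% (6) | 114 | 57 | 42.4–57.6% | 57/120 = 47.5% |
| 10% (12) | 108 | 54 | 42.2–57.8% | 54/120 = 45.0% |
| 15% (18) | 102 | 51 | 42.0–58.0% | 51/120 = 42.5% |
| 20% (24) | 96 | 48 | 41.7–58.3% | 48/120 = 40.0% |

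Only in the 20% row is the all-enrolled rate outside the reported interval.

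In the other direction, if 60 of all 120 enrolled respond (50%), the primary rate would read 60/114 = 52.6%, 60/108 = 55.6%, 60/102 = 58.8% or 60/96 = 62.5%. These are 2.6, 5.6, 8.8 and 12.5 points higher, against a planned half-width of 7.4 points.

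**3. Relaxing that assumption.** If leavers would have responded at rate q, the all-enrolled rate is (1 − d)·0.50 + d·q. At d = 10%:

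| q | All-enrolled rate |
|---|---|
| 0% | 45.0% |
| 25% | 47.5% |
| 50% | 50.0% |
| 75% | 52.5% |

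The primary rate is too high for the unrestricted population when q is below the on-treatment rate, and too low when q is above it.

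**4. How a participant stopping before Week 16 is handled.**

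| Reason for stopping | Primary | Hybrid (ITT) | Hypothetical (ITT) |
|---|---|---|---|
| Lack of efficacy | Excluded | Baseline value, so non-responder | LOCF |
| AD rescue | Excluded | Missing, then MCMC-MI | LOCF |
| Adverse event or other | Excluded | Missing, then MCMC-MI | LOCF |

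No column counts all three rows as non-response.

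**The case against.** Several stronger readings are tempting, and the documents do not support them.

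- *That the primary population leaves out everyone for whom lebrikizumab failed.* It does not. Non-responders who stay on drug remain in the denominator, and at the anticipated 50% they make up half of it. Low- and mid-potency topicals, and up to 10 days of high-potency TCS, are permitted without removal, so rescue is a late step.
- *That 6.3 is flatly contradicted.* The sentence can be read as a statement about collecting response data. The Schedule of Activities includes EASI and IGA at the early discontinuation visit, so leavers are assessed. What stands is that this is not a Week 16 assessment and does not enter the primary rate, so 6.3 needs clarifying.
- *That the restriction is hidden.* It is stated in the Synopsis, Protocol Section 3, Protocol 9.3.2 and SAP 5.2.1.
- *That the rate necessarily overstates response.* Step 3 of the working shows that the direction depends on how leavers would have responded. That they would respond less is plausible for removals driven by rescue. It is not established for adverse-event, pregnancy or administrative stops.
- *That the supportive analyses do nothing.* Both return leavers to the denominator, and the hybrid counts lack-of-efficacy stops as failures. Under Protocol 7.2, a participant needing rescue leaves before the new agent starts, so LOCF would probably carry forward a non-responder EASI in most such cases. What stands is that LOCF can also carry forward an earlier response, and that the hybrid does not treat rescue as failure.

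It is also fair to say that little formal weight rests on the rate. There is no hypothesis test, and Protocol 9.5 disclaims any decision rule. Responder counts, ITT size and disposition by reason will all be reported, so a reader could do the division. That reader would still lack a prespecified estimate with an interval beside the headline.

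**Conclusion.** The mismatch is real and of moderate importance. The primary rate is valid for its disclosed conditional estimand. It does not by itself answer the unrestricted objective, for which it is likely too high when leavers respond less often than completers.

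The size is unknown, because neither document gives a dropout or rescue rate. On the assumption of 5% to 20% leaving, all counted as non-responders, the gap is 2.5 to 10 points below a 50% on-treatment rate. Up to 15% leaving, the all-enrolled figure stays within the reported 90% CI. If early stopping is as rare as Protocol 7.2 expects, the gap will be small. For context, Protocol 2.3 gives 1.4% adverse-event discontinuation on lebrikizumab over 16 weeks in the two monotherapy trials, but that covers one reason only and a different population.

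**What to change.** 1. **Add a supportive composite estimand to SAP 5.2.2.** Population: full ITT. Anyone without an on-treatment Week 16 EASI, for whatever reason, counts as a non-responder. Report the rate with a 90% Wilson CI beside the primary result. Add the row to Table KGBO.5.2 and update the count of estimands in SAP 5.2. Protocol Section 3 already allows further estimands in the SAP.
2. **In the hybrid estimand, group discontinuation for AD rescue with lack of efficacy** (composite), in Table KGBO.5.2 and in SAP 5.4.3. The same column governs the Week 24 hybrid row, so state whether the change applies there too.
3. **Align the wording** of the Synopsis purpose statement and Protocol 6.3, so that both say the primary rate applies to participants who remain on treatment to Week 16.

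The primary estimand and the clinical rules need not change, and no new data are required. The cost is one more table, some text edits, and a lower rate shown beside the headline. Counting adverse-event, administrative and missing cases as failures is a conservative choice, so the new figure should be labelled as the low end for all enrolled.

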6.4. Study Intervention Compliance

Study intervention will be administered under medical supervision by the investigator or designee at the baseline (Week 0, Visit 2) and Week 2 (Visit 3) visits. The dose of study intervention and study participant identification will be confirmed prior to dispensing study drug. The date and time of each dose administered will be recorded in the source documents and will be provided to the sponsor as requested.

Beginning Week 4 (Visit 4) the participant/caregiver will be encouraged to administer the study intervention while in the clinic or at home. Participants may choose to continue to receive study drug injections administered by trained clinic staff for any visit occurring in the clinic. Home dosing must be self-administered or given by a caregiver that has received proper injection technique training.

When participants self-administer study intervention(s) at home, compliance with study intervention will be assessed at each visit. Compliance will be assessed by direct questioning, counting returned injection supplies, and documented in the source documents.

A record of the number of lebrikizumab injections supplies dispensed to and administered by each participant or caregiver must be maintained and reconciled with study intervention and compliance records.

